At least 50% of patients enrolled will be CKD patients. CKD patients must have a documented history of CKD.

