6.2 Patient demographics/other baseline characteristics

Patient demographic and baseline characteristic data to be collected on all patients include date of birth, sex, race and ethnicity, height, weight, and head circumference.

Relevant medical history/current medical condition data includes data until the start of study drug. Where possible, diagnoses, and not symptoms will be recorded. Patients with CKD as defined in [Section 4](#) should have a corresponding medical history of chronic kidney disease etiology recorded.

Visit 1

At Visit 1, the investigator or investigator's staff will call into IRT and register the patient. During this call, the patient's date of birth, gender, CKD status, and body weight will be entered into the IRT, along with the patient number.

Visit 2

The patient is enrolled into the trial at Visit 2 once all eligibility criteria are met (within 28 days of Visit 1). At this visit, the investigator or investigator's staff will call into IRT and enter the patient's body weight and CKD status.

CKD status, age and region

At Visit 2, the investigator or staff will also enter the patient's CKD status (CKD or non-CKD patient). The CKD definition is discussed in [Section 4](#). At least 50% of the patients enrolled into the trial must have CKD. IRT will be used to track CKD status at Visit 2. IRT will be used to prevent over enrollment of non-CKD patients, in order to ensure that a sufficient number of CKD patients are enrolled (e.g. should enrollment of 65 non-CKD patients be achieved, IRT will not permit enrollment and assignment of study drug to further non-CKD patients in the study). Patients will be stratified by CKD status.

Visit 2 to Visit 10

The IRT system will be called at every visit. Study medication number assignment will be at every dispensing visit (Visit 2-Visit 10). The dose of medication that the patient receives will be based on the patient's weight at Visit 2 for double blind, and at Visit 5 and Visit 8 during the open-label phase.

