Percentage of patients achieving MSBP < 95th percentile for age, gender and height at Week 6 endpoint will be also analyzed using a logistic regression model with treatment and CKD strata as factors and baseline MSBP as the covariate. The odds ratio of Valsartan 4.0 mg/kg / Valsartan 0.25 mg/kg will be computed, along with the associated 95% confidence interval and p-value. In addition, the number (and %) of patients achieving MSBP < 95th percentile for age, gender and height will be summarized by treatment and visit (including the Week 6 endpoint). Similar analyses will be carried out for the CKD and non-CKD subgroups of patients.

Percentage of patients achieving both MSBP and MDBP < 90th percentile for age, gender and height; percentage of patients achieving both MSBP and MDBP < 95th percentile for age, gender and heights.

Percentage of patients achieving both MSBP and MDBP < 90th percentile for age, gender and height at Week 6 endpoint will be analyzed using a logistic regression model with treatment and CKD strata as factors and baseline MSBP as the covariate. The odds ratio of Valsartan 4.0 mg/kg / Valsartan 0.25 mg/kg will be computed, along with the associated 95% confidence interval and p-value. In addition, the number (and %) of patients achieving both MSBP and MDBP < 90th percentile for age, gender and height will be summarized by treatment and visit (including the Week 6 endpoint). Similar analyses will be carried out for the CKD and non-CKD subgroups of patients.

Similar analyses will be also performed for the percentage of patients achieving both MSBP and MDBP < 95th percentile for age, gender and height at Week 6 endpoint.

UACR (Urine Albumin Creatinine Ratio) in CKD patients

UACR was collected for CKD patients only. The UACR value at a given visit for a patient is to be derived by the median of the three lab values collected for that visit. The UACR value will be assessed in the CKD patients.

Change from baseline in log(base 10)-transformed UACR will be analyzed using an ANCOVA model with treatment as a factor and log (base 10)-transformed baseline UACR as a covariate. The estimated treatment effects, treatment difference, 95% confidence interval, and p-value for the treatment comparison will be provided. The estimates to be presented will be in back-transformed scale.

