Instead of the specified % change from baseline in UACR $\leq 25\%$ in the protocol, the UACR response is to be defined as a percentage reduction from baseline in UACR $\geq 25\%$. The proportion of patients with UACR response at Week 6 endpoint (LOCF) will be analyzed using a logistic regression with treatment as a factor and baseline UACR as a covariate. The odds ratio of Valsartan 4.0 mg/kg / Valsartan 0.25 mg/kg will be computed, along with the associated 95% confidence interval and p-value.

Summary statistics (n, mean, standard deviation, median, min, max, geometric mean) of the UACR values for baseline, Week 6 endpoint and the respective change (from baseline at Week 6 endpoint) will be provided by treatment group. The number and percent of patients will be summarized by treatment group for each of the following categories in change from baseline at Week 6 endpoint: $\geq 25\%$ reduction, change is less than 25% in positive/negative direction, and $\geq 25\%$ increase. Similar summary will be also provided by treatment group for the following categories: $\geq 50\%$ reduction, change is less than 50% in positive/negative direction and $\geq 50\%$ increase.

Cystain C GFR (Glomerular filtration rate) in CKD patients

cGFR (Cystain C GFR) was collected and assessed for CKD patients only.

Change from baseline in log(base 10)-transformed cGFR will be analyzed using an ANCOVA model with treatment as a factor and log(base 10)-transformed baseline cGFR as a covariate. The estimated treatment effects, treatment difference, 95% confidence interval and p-value for the treatment comparison will be provided. The estimates to be presented will be in back-transformed scale.

Summary statistics (n, mean, standard deviation, median, min, max, geometric mean) of the cGFR values for baseline, Week 6 endpoint and the respective change (from baseline at Week 6 endpoint) will be provided by treatment group.

Period 2

The efficacy data during the open-label period 2 will be assessed based on the summary statistics and plots below in OFAS. The summaries and plots will be presented with one single arm including all patients evaluated in the open-label period 2.

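### The UACR responder model adjusts for untransformed baseline UACR while the ANCOVA of the same variable uses log10 baseline; log10 should be used in both (minor)

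*SAP*

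**What the plan says.** SAP 9.7.1.2.2, under UACR in CKD patients, sets out two treatment comparisons of the same measurement at the end of the double-blind period.

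- **Continuous.** Change from baseline in log10 UACR is analysed "using an ANCOVA model with treatment as a factor and log (base 10)-transformed baseline UACR as a covariate", with estimates back-transformed.
- **Responder.** The SAP replaces the protocol's criterion: "the UACR response is to be defined as a percentage reduction from baseline in UACR" of at least 25%. The proportion responding at the Week 6 endpoint is analysed "using a logistic regression with treatment as a factor and baseline UACR as a covariate", and an odds ratio, 95% confidence interval and p-value are reported.

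The visit value is "derived by the median of the three lab values collected for that visit". The population is restricted: "UACR was collected for CKD patients only". Protocol 9.5.1 lists UACR response among the key secondary variables.

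The SAP gives no reason for the two baseline scales. The sample logistic code in SAP 10.3 does not settle the matter. Its `base` term is defined only for blood pressure, and the section says the code actually used may differ.

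**The concern.** Read literally, the responder model uses raw UACR. Elsewhere the SAP treats UACR as skewed: it takes logs for the ANCOVA, back-transforms the estimates and reports geometric means. A wide spread is also plausible from eligibility. Protocol 4.1 lets CKD be established by urine, imaging or biopsy findings or by reduced eGFR. Protocol 4.2 admits stable renal transplant recipients. Neither section limits UACR.

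Two things follow if baseline is prognostic and the relation is on the log scale.

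1. A linear term in raw UACR fits that relation poorly, so part of any chance baseline difference between arms stays in the treatment estimate.
2. The baseline slope leans on the few children with the highest values.

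At stake is the quality of the adjustment for one secondary odds ratio. There is also a reproducibility issue, because an analyst who reads the covariate as raw and one who assumes log10 would report different odds ratios.

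**Working it through.** **The plan's own figures.** The documents give no planning figure for the UACR responder analysis. The only computable one is the overall sample size, and it holds: 116 / 0.9 = 128.9, or 129 against the stated 130. With 58 per arm, a difference of 6 mmHg and SD 11 mmHg, power is 83.6% (normal approximation), which meets the stated minimum of 80%.

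**Number of children.** Protocol Section 4 states "At least 50% of patients enrolled will be CKD patients". Protocol 6.2 stops non-CKD entry "should enrollment of 65 non-CKD patients be achieved". So at least 130 − 65 = 65 CKD children are randomized. Half of the 116 completers is 58.

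**Why the log scale fits the outcome.** A reduction of at least 25% means UACR at Week 6 / UACR at baseline ≤ 0.75. That is the same as log10(Week 6) − log10(baseline) ≤ log10(0.75) = −0.125. Response is therefore a cut on the same log change that the ANCOVA models with log10 baseline.

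**Assumptions for the size.** None of these is in the documents. Baseline UACR is log-normal with log10 SD 0.3, 0.5, 0.75 or 1.0. The control response rate is about 30%. The treatment odds ratio is 1 or 3. The baseline log-odds slope is 0 (with OR 1), or 0.5 or 1.0 per SD of log10 UACR (with OR 3). There were 58 or 65 children, randomized 1:1, and 800 simulated trials per setting. Each trial was fitted with raw and with log10 baseline.

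| Assumed log10 SD | Top two children's share of raw covariate sum of squares | Max leverage, raw | Max leverage, log10 | Change in treatment log-OR, raw vs log10: median (90th pct), in SE | Power at OR 3, raw → log10 (slope 0.5; slope 1.0) |
|---|---|---|---|---|---|
| 0.3 | 38–40% | 0.13–0.24 | 0.10–0.15 | 0.04–0.10 (0.12–0.24) | 45.9 → 46.3%; 46.3 → 47.1% |
| 0.5 | 55–57% | 0.17–0.32 | 0.10–0.14 | 0.05–0.15 (0.17–0.41) | 50.2 → 51.2%; 41.0 → 42.2% |
| 0.75 | 71–74% | 0.22–0.40 | 0.10–0.14 | 0.07–0.18 (0.20–0.51) | 49.1 → 50.6%; 42.1 → 44.4% |
| 1.0 | 84–85% | 0.28–0.47 | 0.11–0.15 | 0.08–0.22 (0.23–0.61) | 47.7 → 48.6%; 41.0 → 42.0% |

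On the log10 scale the top two children hold 18–20% in every setting.

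**Deleting the two children with the highest UACR.**

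- Baseline slope, when baseline is not prognostic: median shift 0.56–1.14 SE raw, 0.31–0.35 SE log10.
- Baseline slope, when it is prognostic: 0.07–0.80 SE raw, 0.22–0.34 SE log10.
- Treatment log-OR, all settings: median 0.01–0.10 SE raw (90th percentile 0.27–0.35), 0.05–0.14 SE log10 (90th percentile 0.23–0.34).

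**Type I error** (OR 1, slope 0): 3.0–4.8% on both scales.

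**Chance imbalance.** A separate simulation with 64 CKD children and assumed log-normal UACR related the estimated treatment log-OR to the between-arm difference in mean log10 baseline. The raw model leaves a dependence of about 0.13–0.33 per SD of log10 UACR, and the log10 model about 0. With 32 per arm the typical chance difference is √(2/32) = 0.25 SD. That leaves 0.25 × 0.13 = 0.03 to 0.25 × 0.33 = 0.08 on the log-OR, or about 3–9% on the odds ratio. In that simulation power rose 0.6–1.3 points, the significance verdict changed in about 4–6% of trials with a true effect, and type I error was about 5% on either scale.

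**The case against.** The strongest defence is that the two models need not share a covariate scale. The ANCOVA's response is log change, so log baseline follows from it. Logistic regression has a binary response and assumes nothing about the distribution of its covariate. The comparison is randomized and stratified by CKD status, the baseline slope is a nuisance parameter, and the treatment odds ratio is what gets reported. The SAP also offers other views of the same data: the log-scale ANCOVA, the median of three samples, geometric means, and response counts at the 25% and 50% thresholds. Protocol 9.8 plans no power for key secondary variables.

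Much of this stands. The different scales are not a contradiction, and the trial's conclusions do not hang on this model. It does not make raw baseline the better choice, since the outcome is itself defined by a ratio.

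A reader might infer more: that one or two heavily proteinuric children drive the adjustment, or that they dominate the odds ratio. The documents do not support either inference. They give no baseline UACR mean, SD or range. At an assumed log10 SD of 0.3 the top two children hold less than half of the raw sum of squares. That share is also an unweighted measure of the covariate's spread, so it does not measure influence on the treatment effect. Deleting those children moves the treatment log-OR about equally little on either scale.

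**Conclusion.** The point holds as a minor one. The responder model names untransformed baseline UACR without giving a reason, and log10 suits a ratio-defined response better. The expected gain is about 0–2 power points (the largest simulated difference was 2.3) and more complete removal of chance baseline imbalance. Type I error does not change.

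The choice of scale can still move the reported estimate. The median change is 0.04–0.22 SE, and the 90th percentile reaches 0.61 SE in the most skewed setting with a strongly prognostic baseline. These differences show that the models disagree; they do not show that the raw model is invalid. That is enough reason to fix the scale before unblinding.

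All sizes rest on assumed log-normal UACR, response rates and baseline slopes. Log-normality favours the log10 covariate, so the gains should be read as what to expect if UACR behaves as the SAP's own log transformation implies.

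**What to change.** In SAP 9.7.1.2.2, name log10-transformed baseline UACR as the covariate in the UACR responder logistic regression, as the ANCOVA already does. If raw baseline is intended, state the reason. Add a line to SAP 10.3 saying that the baseline term in the UACR logistic model is log10 baseline UACR, because the sample code covers blood pressure only.

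The cost is one phrase and one line. The variable already has to be derived for the ANCOVA, no new data are needed, and the calculations showed no inflation of type I error or loss of power. The change should be made before unblinding.

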3.2 Rationale of study design

Two previous valsartan trials in hypertensive children between 6 months and 5 years showed mixed results with one study demonstrating a trend toward a positive dose response and the other not. Following consultation between the PDCO and the EMA committee CHMP, the CHMP indicated that the reasons behind the inconsistent results in the younger age group were not entirely understood and that no clear approach exists in the design of clinical trials for antihypertensive agents in the pediatric population. The CHMP recognized the clinical need in this age group and that it would be relevant to conduct a new study. The CHMP's Scientific Advice Procedure with the involvement of the PDCO was initiated for protocol assistance ([REDACTED]). Ultimately, an overall study design agreement was reached to perform an additional study in 1 to 5 year old children with hypertension using a similar design as in a previous study ([REDACTED]).

The study would consist of three periods. The first would be the Screening period, followed by a six-week randomized (1:1 ratio), double-blind, double-dummy dose-ranging period consisting of 2 valsartan dose groups (0.25 mg/kg and 4 mg/kg). The study would conclude with a 20 week open-label titration phase. All patients will be placed on a stabilized dose after the double-blind period (valsartan 1 mg/kg), with 3 optional titration steps during the open-label phase. The intent is to investigate the interrelation between the required starting dose

[REDACTED]

and potential risk factors. Duration of 26 weeks was selected as it is considered to provide the most appropriate time course to study proteinuria.

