6.3 Treatment exposure and compliance

Study medication and concomitant therapies will be recorded on the Dosage Administration CRF, the Concomitant medication/significant therapies prior to study drug administration CRF, and the concomitant medications/significant non-drug therapies after study drug administration CRF.

Patient compliance with the study drug treatment will be assessed by the investigator and/or study personnel using pill count, information from the patient/caregiver and drug accountability. This information should be captured in the source documents and in the CRF. Patient compliance should be at least 75% during the study. The investigator and/or study personnel will counsel the patient on proper method of taking the study drug as appropriate to ensure compliance during the trial. Patients who miss study drug for 2 weeks consecutively or more should be discontinued.

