9.4.4 Supportive analyses

In addition to the primary analysis based on the FAS population, a similar analysis will also be performed on the PPS population as a supplementary assessment.

To further assess the dose response, an analysis of covariate (ANCOVA) will be performed on the change from baseline at Week 6 endpoint in MSBP with CKD strata as a factor, dose per body weight as the main regressor, and baseline MSBP as a covariate. The analysis will be performed for the FAS population. The least-squares mean estimate for the slope will be provided.

The change from baseline in MSBP during double-blind period will be summarized by treatment and study week for the FAS and PPS populations respectively.

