9.5.2 Efficacy variables

To evaluate the overall blood pressure changes for patients treated with valsartan throughout the study, the change from baseline (Week 0) in MSBP at the end of study will be summarized by open-label visits for OFAS population. A similar summary will be provided for MDBP.

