In addition to the primary analysis based on the FAS population, a similar analysis for the primary endpoint will also be performed on the PPS population as a supplementary assessment.

To further assess the dose response, the change from baseline at Week 6 endpoint in MSBP will be analyzed in FAS by an analysis of covariance model with CKD strata as the factor and baseline MSBP as a covariate, and dose per body weight (mg/kg) as the main regressor. The estimated slope with 95% confidence interval and p-value for the dose per body weight will be provided.

Subgroup analysis for CKD/non CKD patients

Similar analysis of the primary efficacy variable for the treatment comparison will be performed for the subgroup of CKD patients and for the subgroup of non-CKD patients (per CKD yes/no strata). The estimated treatment difference, 95% confidence interval and two-sided p-value for the treatment comparison within each subgroup analysis will be provided. Furthermore, treatment-by-CKD strata interaction in the entire FAS will be assessed by inclusion of the additional interaction term to the primary analysis model for the overall analysis in FAS and the p-value for the respective interaction term will be provided.

Descriptive statistics

The change from baseline in MSBP (together with the corresponding baseline and post-baseline MSBP) during double-blind phase will be summarized by treatment and visit (including Week 6 LOCF endpoint) for the FAS (for overall as well as for each of the CKD/non-CKD subgroup). The MSBP will be plotted versus visit (not including Week 6 LOCF endpoint) by treatment group for the FAS (for overall as well as for each of CKD/non-CKD subgroup). In addition, change from baseline in MSBP will also be plotted versus visit by treatment group for the FAS (for overall as well as for each of CKD/non-CKD subgroup).

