1. Change from baseline (Visit 2) in MSBP (together with the corresponding baseline and post-baseline MSBP) will be summarized (with n, mean, standard deviation, median, min, and max) by visit (including LOCF endpoint at end of the open-label period 2) during the open-label period 2. Similar summary will be provided for MDBP. Similar summaries for MSBP and MDBP will also be provided for the CKD and non-CKD subgroups. In addition, similar plots as for MSBP/MDBP in the double-blind period will be provided with one single arm for the OFAS in the open-label period 2.
2. Percentage of patients achieving MSBP $< 90^{\text{th}}$ percentile (as well as MSBP $< 95^{\text{th}}$ percentile, both MSBP/MDBP $< 90^{\text{th}}$ percentile, and both MSBP/MDBP $< 95^{\text{th}}$ percentile) for age, gender and height will be summarized by visit during the open-label period 2.

label period 2. In addition, similar summaries will be provided for the CKD and non-CKD patients

3. In the CKD patients, change from baseline in UACR (together with the corresponding baseline and post-baseline UACR) will be summarized (with n, mean, standard deviation, median, min, max and geometric mean) by visit during the open-label period 2. In addition, the n and percentage of CKD patients in the categories of UACR changes (as defined in the assessment during the period 1) will be provided by visit during the open-label period 2.
4. In the CKD patients, change from baseline in cGFR (together with the corresponding baseline and post-baseline cGFR) will be summarized (with n, mean, standard deviation, median, min, max and geometric mean) by visit during the open-label period 2.

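### Should open-label blood pressure be shown by former randomised arm, and does the dose slope add anything to the primary test?

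*SAP*

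**What the plan says.** Protocol 3.1 starts every child entering Period 2 on 1 mg/kg at Visit 5 (Week 6), with optional up-titration from Visit 7 (Week 10). Visit-day doses follow the assessments (Protocol 5.5.4) and blood pressure is read at every visit (Table 6-1, footnote 7). Visit 5 is therefore the last reading on the randomised dose, and Visits 6 and 7 are the readings on the common 1 mg/kg step.

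Protocol 3.2 gives the titration phase a purpose: "The intent is to investigate the interrelation between the required starting dose". The sentence is then partly blacked out and resumes with potential risk factors.

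Protocol 9.5.2 wants overall blood pressure change on valsartan across the study, and says it "will be summarized by open-label visits for OFAS population". SAP 9.7.1.2.2 (Period 2) implements this as: "The summaries and plots will be presented with one single arm including all patients evaluated in the open-label period 2". Item 1 of that list, "Change from baseline (Visit 2) in MSBP", is tabulated by visit, with MDBP treated alike and both repeated by CKD status. No output is split by former arm.

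For the dose slope, Protocol 9.4.4 names "dose per body weight as the main regressor" and SAP 9.7.1.2.1 (Supportive analyses) names "dose per body weight (mg/kg) as the main regressor". Neither says whether assigned or actual dose is meant. Outcome, analysis set, CKD factor and baseline covariate match the primary ANCOVA.

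**The concern.** The two arms reach 1 mg/kg from opposite sides. If four weeks is not long enough for the earlier dose to wear off or the new one to take full effect, the children from 4 mg/kg would still read low at Visit 7 and those from 0.25 mg/kg would still read high. A single column averages the two and hides the gap. The protocol allows six weeks in Period 1 for the maximum effect to be reached, so incomplete adjustment at two or four weeks is conceivable. At stake would be the reading of blood pressure and control rates on the open-label starting dose.

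The slope raises a different worry. It is offered as a further look at dose response, and the SAP attaches a p-value. With only two assigned doses, a reader might take that p-value as a second piece of evidence, in an age group where earlier trials gave inconsistent dose-response results (Protocol 1.1).

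**Working it through.** **Inputs.** Difference 6 mmHg, SD 11 mmHg, 116 completers at 1:1, so 58 per arm (Protocol 9.7, SAP 9.7.2). Carry-over fractions, between-visit correlations and dose variation are not in the documents and are assumed ranges below.

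**The plan's own figure.** With 58 per arm, power for 6 mmHg at SD 11 is 83.6% (normal approximation) or 83.0% (t test). The stated minimum of 80% is met; 54 per arm would do by the t test.

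**What pooling hides.** Let a be the mean on 4 mg/kg minus the mean on 1 mg/kg, b the mean on 0.25 mg/kg minus the mean on 1 mg/kg, and c the fraction of the earlier effect still present at Visit 7. With b − a = 6 and equal arms:

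- gap between former arms = c(b − a) = 6c
- shift of the pooled mean = c(a + b)/2

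If response is linear in log dose, 1 is the geometric mean of 0.25 and 4, so a = −3, b = 3 and the shift is 0. If it is linear in dose, a = −6 × 3/3.75 = −4.8 and b = 6 × 0.75/3.75 = 1.2, so the shift has size 1.8c. The worst monotone case puts the whole effect on one side of 1 mg/kg, giving 3c.

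| c (assumed) | Gap, mmHg | Shift, log dose | Shift, linear dose | Shift, worst case |
|---|---|---|---|---|
| 25% | 1.5 | 0 | 0.45 | 0.75 |
| 50% | 3.0 | 0 | 0.90 | 1.50 |
| 75% | 4.5 | 0 | 1.35 | 2.25 |

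The pooled SD would not reveal the gap: √(11² + d²/4) is 11.2 for a gap d of 4 mmHg and 11.4 for 6 mmHg.

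**What by-arm columns would show.** The 95% half-width for the Visit 7 gap is t × 11 × √(2/58) = 4.05 mmHg. It runs from 2.9 to 5.5 mmHg over an assumed SD of 8 to 14 and 52 to 58 per arm. Power to detect a residual gap is 16% at 2 mmHg, 50% at 4 mmHg and 84% at 6 mmHg. A chance Week 6 gap also shrinks: after baseline adjustment with equal correlation r between visits, 6r/(1 + r) remains at Visit 7. That is 1.4 mmHg at r = 0.3 and 2.8 mmHg at r = 0.9, the same as 23% to 47% true carry-over.

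**The slope.** With T = 1 for the high-dose arm, assigned dose = 0.25 + 3.75T. The dose model is the primary model with one column rescaled, so slope and standard error are both divided by 3.75 and t and p are unchanged. A 6 mmHg difference becomes 6/3.75 = 1.6 mmHg per mg/kg. One simulated dataset gave t = 3.619 in absolute value and p = 0.00044 from both models.

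For actual dose, Protocol 6.3 sets an expectation: "Patient compliance should be at least 75% during the study". With compliance spread evenly over 75% to 100%, slope and primary gave the same verdict at 0.05 in 99.1% of 4,000 simulated trials with no effect and in 97.35% with a 6 mmHg effect (baseline SD 8, assumed). With 20% random dose variation the figures were 97.2% and 93.0%. A separate simulation of 500 trials per setting with a 6 mmHg effect found agreement of 99.4%, 98.6%, 95.4% and 91.4% at 2%, 5%, 10% and 20% variation.

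**The case for a change.** The best case for a change is that it costs almost nothing. Former arm and blood pressure at every visit are already in the data, Protocol 9.5.2 does not require pooling, and a few descriptive columns would keep the randomised comparison visible when both groups are on the same dose. Visit 7 is also where the first titration decision is made, and one sentence would define the dose variable.

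Some of this stands. The gap is not displayed, the CKD split does not help to show it, and the regressor is undefined. The rest is weaker.

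- The aim in Protocol 9.5.2 is overall change, which a single column by visit delivers. Adverse events are likewise split by treatment only in the double-blind period (Protocol 9.5.3, SAP 9.7.1.3.1).
- Visit 5 by arm is already planned in the Period 1 summaries (SAP 9.7.1.2.1, Descriptive statistics), so only Visits 6 and 7 would be new.
- The legible part of the sentence in Protocol 3.2 concerns how starting dose relates to risk factors. It does not promise an estimate of blood pressure on 1 mg/kg free of carry-over.
- No carry-over figure is given. The nearest benchmarks are the 28-day washout for earlier RAAS blockers and the four-week titration steps (Protocol 3.1). Visit 7 falls on Day 70, 28 days after Visit 5 on Day 42. This does not prove that carry-over is nil, but it gives no support for a large one.

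**Conclusion.** No change is needed. Pooling Period 2 over the former arms is a fair choice for a descriptive open-label phase added mainly for safety (Protocol 1.2), and the Week 6 primary comparison is untouched. Under an assumed 6 mmHg effect and 25% to 75% carry-over, the table would hide a gap of 1.5 to 4.5 mmHg and its mean would be off by at most 2.25 mmHg. By-arm columns, with a half-width near 4 mmHg, could neither establish nor exclude a gap of that size, and they could not separate carry-over from the fading of a chance difference. They can be produced later from existing data if someone wants them.

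The slope is a rescaling of the primary contrast, listed as supportive and given no share of the significance level. Reporting an effect per mg/kg is legitimate so long as its p-value is not counted as a second result. Whether assigned or actual dose is used can be settled when the analysis is programmed: the verdict is identical to the primary on assigned dose and nearly always the same on actual dose. This rests on the sample-size SD of 11 mmHg applying at Visit 7, near-equal arms entering Period 2, and a monotone dose response.
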